10.4.2 Analysis of secondary variables

Secondary variables will be analyzed using standard descriptive statistical methods listed in section 10.2.

10.5 Statistical analysis of safety

The safety and tolerability assessments will be evaluated using the following data:

1. Outcome of adverse events
2. Clinical examination

10.5.1 Analysis of adverse events

Distinctions will be made between the adverse events not related to the study treatment, the technical procedure or the study device, and those related to any of the above.

Numbers and frequencies of AEs will be tabulated and the proportions of patients exhibiting each AE will be displayed. The adverse events will be classified according to the MedDRA nomenclature. The treatment-emergent adverse events (which happen or worsen after the first study drug intake) will be summarised by System Organ Class (SOC) and preferred term. In addition, the adverse events will be classified according to the National Cancer Institute (NCI) Common Terminology Criteria for Adverse Events (CTCAE) which is a safety endpoint of the study. Tabulations will also be made for the System Organ Class (SOC, current MedDRA version), intensity, relationship, seriousness, and attribution corresponding to each AE. Separate tabulations will be made for SAEs.

The treatment-emergent adverse events (which occurred or worsened after the first study drug intake) will be summarised by primary SOC system and preferred term.

For pre-treatment events listings will be provided. For medical/surgical history and additional examinations listings will be provided.

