6.3 TOOKAD® Soluble VTP treatment procedure

6.3.1 Overview of procedure

The VTP procedure²⁶ will consist of a single, 10 minute infusion of 4mg/kg TOOKAD® Soluble. The drug will be activated by laser light at 753nm, with a dose of 200J/cm, and a fixed power of 150mW/cm, given over 22min 15s and delivered using interstitial optical fibers, inserted using a transperineal route, into the prostate gland:

1. A transperineal template is used for the placement of the transparent catheters which are positioned in the prostate under transrectal ultrasound image guidance.
2. The optical fibers are then inserted into the catheters.
3. The drug infusion begins once the catheter positioning is finalized.
4. The light delivery begins immediately after the completion of the drug infusion.

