6.3.4 Procedures carried out in the operating-room

Light delivery catheter insertion:

Subjects will be placed in the lithotomy position and will remain in this position throughout the procedure. A Foley catheter is placed in the bladder prior to the procedure, and removed at least 6 hours after the procedure. TRUS images are used to visualize the prostate and to define the treatment guidance using TOOGUIDE TRUS.

A transperineal template is used to guide the placement of the flexible hollow introduction catheters into the prostate. These have a metal inner mandrel to aid insertion. This procedure is similar to that used routinely for high dose rate (HDR) brachytherapy of prostate cancer.

Following satisfactory positioning of the introduction catheter the metal mandrel is removed and replaced with a cylindrically diffusing optical fiber. The length of the diffusing part of the fiber is chosen according to the treatment guidance based on the ultrasound images of the prostate. Fibers are available with illuminating fiber lengths of 1 - 5 cm, in 0.5 cm increments.

Laser:

The lasers to be used for the procedure (Intermedic, Spain) are connected to the optical fibers, once the optical fibers are satisfactorily positioned within the flexible introduction catheters.

Light detection:

One light detecting probe will be placed in the rectum to ensure that the light dose is sufficiently low. The prostate is illuminated prior to drug injection and the light measured. If the light in the rectum exceeds 13 mW/cm² then the optical fibers in the prostate will be repositioned.

Drug delivery:

The infusion puncture site should be placed in a large vein at the top of the forearm. The infusion will be conducted using automatic syringes, through a fast flow peripheral line (antecubital catheter). The Sponsor will provide the study centre with the appropriate infusion devices. Infusion will be over 10 minutes. The choice for size of intravenous catheter will be left up to the discretion of the involved medical

team who will be responsible for ensuring that the catheter is flushed and working properly prior to starting infusion.

Light delivery:

The light delivery will begin once the drug infusion has ended. Light will be delivered at an energy dose of 200 J/cm with a power of 150 mW/cm over 22min 15s.

See appendix 6 "VTP procedure Book".

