10.2.2.4 Intention-to-treat, per protocol and safety populations

All descriptive statistics will be shown on all patients enrolled in this study, for whom CRF at entries are available irrespective of protocol deviations (**intention-to-treat population**). Safety data will be analyzed using all patients who have received any amount of TOOKAD® Soluble or have started any part of the VTP procedure, including anesthesia (**safety population**).

Descriptive statistics will also be shown using all patients who comply with the study protocol (**per-protocol population**). The per protocol population of efficacy will consist of all patients who:

1. complied with the protocol for inclusion criteria and exclusion and follow-up,

2. received the appropriate dose of TOOKAD® Soluble, LDI and energy delivered and underwent the VTP procedure, receiving the ascribed dose of TOOKAD® Soluble and light,
3. had no major protocol deviations.

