#### **Adverse events**

Distinctions will be made between the adverse events not related to the study treatment, related to the study treatment or related to the technical procedure of the VTP. Frequencies of AEs will be tabulated by treatment arm and the proportions of patients exhibiting each AE will be displayed. The adverse events will be classified according to MedDRA version 23.1 or higher.

The treatment-emergent adverse events (adverse events starting after the treatment) will be summarized by System Organ Class (SOC) and preferred term. In addition, the adverse events will be classified according to the NCI Common Terminology Criteria for Adverse Events which is a safety end point of the study. Tabulations will also be made for the System Organ Class, intensity, relationship, seriousness, and attribution corresponding to each AE. Separate tabulations will be made for SAEs.

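### The treatment-emergent window opens at first drug intake (protocol) or at an undefined point after treatment (SAP), but the safety population opens at anaesthesia, so procedural events that begin before the first infusion miss the treatment-emergent table.

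*Protocol*

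**What the plan says.** **Start of the window.** Protocol 10.5.1 defines treatment-emergent events, twice, by reference to first drug intake: "The treatment-emergent adverse events (which happen or worsen after the first study drug intake) will be summarised by System Organ Class". The SAP, under Adverse events, has: "The treatment-emergent adverse events (adverse events starting after the treatment) will be summarized by System Organ Class (SOC) and preferred term". It does not say whether this means after the start or the end of treatment, and it has no provision for worsening.

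**Population.** Protocol 10.2.2.4 includes in the safety population men who received any drug or who "have started any part of the VTP procedure, including anesthesia". The SAP's safety population is equivalent and also names the initiation of anaesthesia.

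**Order of steps.** Protocol 6.3.4: "A Foley catheter is placed in the bladder prior to the procedure". Protocol 6.3.1, after the introduction catheters are placed: "The optical fibers are then inserted into the catheters". Then: "The drug infusion begins once the catheter positioning is finalized". Section 6.3.4 also has a test illumination before the drug is given.

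**Events before treatment.** Protocol 10.5.1: "For pre-treatment events listings will be provided". Neither document defines the term.

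**Relatedness.** Protocol 9.3 records drug-, device- and procedure-related events as separate classes, and 10.5.1 names all three in its distinction. The SAP has: "Distinctions will be made between the adverse events not related to the study treatment, related to the study treatment or related to the technical procedure". It gives no device class.

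**The concern.** The study treatment is a drug, a laser and an invasive procedure under general anaesthesia. Protocol 9.2 makes anaesthesia, the insertion, positioning and removal of the catheters, and urinary catheterisation part of the procedure for adverse event assessment. Several of these steps are complete before any drug is given, so a window that opens at drug intake starts too late for part of the treatment under study.

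What is at stake is the treatment-emergent summary, the only table that both documents expressly assign to System Organ Class and preferred term. Followed as written, it omits some events that the plan itself regards as study-related, and it uses a population defined by a different starting point.

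**Working it through.** The point turns on definitions and the order of events. The plan gives no figure to reproduce.

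**Step 1: order of events.** From protocol 6.3.1, 6.3.4 and 6.4.2, anaesthesia, the Foley catheter, introduction catheters, fibres and test illumination all precede the infusion. The infusion is followed by illumination and then recovery. The safety population opens at anaesthesia and the protocol's treatment-emergent window opens at the infusion.

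**Step 2: apply each definition to the possible onsets.**

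| Onset of event | Protocol 10.5.1 | SAP, Adverse events |
|---|---|---|
| After induction, before first infusion, no later worsening | Not counted | Not counted |
| Same onset, worsens after the infusion starts | Counted | Not counted (no worsening rule) |
| During first infusion or illumination | Counted | Depends on whether treatment means its start or its end |
| After illumination | Counted | Counted |
| Between induction and infusion of a re-treatment | Counted (first drug intake has passed) | Unclear which treatment is meant |

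The first and last rows show the inconsistency. Protocol 6.4.10 performs re-treatment under the same conditions as the first procedure, yet an identical insertion injury counts only the second time. The SAP also plans a separate safety analysis of re-treated men, so the difference would carry into that comparison.

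**Step 3: length of the uncounted interval.** Infusion plus illumination is 10 + 22.25 = 32.25 minutes (protocol 6.3.1). The whole procedure lasts 90 to 120 minutes (Synopsis). The remainder is 90 − 32.25 = 57.75 to 120 − 32.25 = 87.75 minutes, or 64% to 73% of the total. The documents do not divide this between the time before infusion and the time after illumination, so the length of the uncounted interval is unknown.

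**Step 4: denominator.** Let N be the safety population, k the men anaesthetised but not dosed, and p the treatment-emergent rate among dosed men. The reported rate is p × (N − k)/N, a relative loss of k/N whatever p is. Take N = 50 (the planned number) and assume p = 30% for illustration:

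- k = 0: 30.0%
- k = 1: 0.30 × 49/50 = 29.4%
- k = 2: 0.30 × 48/50 = 28.8%
- k = 4: 0.30 × 46/50 = 27.6%

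The documents give no value for k or p.

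**Step 5: other tables.** Protocol 10.5.1 and the SAP both tabulate frequencies and patient proportions of adverse events. Both also tabulate each event by System Organ Class, intensity, relationship, seriousness and attribution, and serious events separately. None of these is limited to treatment-emergent events. Collection runs from consent (protocol 9.3), so a pre-infusion event would reach them.

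**The case against.** The strongest reply is that nothing is hidden. The tabulations in step 5 carry pre-infusion events, and the treatment-emergent rule depends on onset, whatever the cause. Harm from anaesthesia or catheter insertion that first appears after the infusion starts is therefore counted under the protocol. Catheter removal also falls after treatment. This stands, and it limits the point to events that begin before the first infusion and, under the protocol, do not later worsen. A reader might infer that procedural harms as a class are left out of the safety results; the documents do not support that.

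Three other inferences also go too far.

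- **That the treatment-emergent table is the main safety result.** Neither document ranks it above the others.
- **That an intra-operative event would only be listed, as a pre-treatment event.** No section classes it so. The term's other use, in protocol 10.2.2.1, sits with medical history, which suggests baseline conditions. What remains is an undefined term.
- **That about 8 of 50 men could be undosed**, by scaling up the 2 of 12 men with 3+4 cancer who were withdrawn before drug in the earlier Latin American study (2/12 × 50 = 8.3). Protocol 2.2.4 does not say that those two men were anaesthetised. They are a subgroup of 81, and the cause, a prior TURP, is excluded here too (protocol 5.3). The figure is not a supported bound.

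On the device class, the SAP still tabulates relationship and attribution for each event and the data are collected. The omission is a gap in wording and does not mean that data are lost.

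**Conclusion.** The mismatch is real and should be corrected. As written, study-procedure events that begin between induction and the first infusion, without later worsening, miss the treatment-emergent table in both documents. The SAP wording is looser still, because it drops worsening and could be read to exclude events during infusion and illumination. The protocol's rule also treats the same event differently at the first procedure and at re-treatment.

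The number of events affected cannot be estimated from the documents. The denominator effect is 2% of the rate for each undosed man in 50. It is probably small, assuming that few men are stopped between anaesthesia and infusion. No safety hypothesis test depends on it. The case for change rests on one summary table that does not match its own population, and on a protocol and SAP that define it differently.

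**What to change.** - **Protocol 10.5.1 (both statements of the definition) and SAP, Adverse events:** define treatment-emergent events as those that start or worsen on or after the start of the first VTP procedure, taken as induction of anaesthesia. This matches the entry point of the safety population and treats first procedures and re-treatments alike.
- **Protocol 10.5.1:** define pre-treatment events as those before that point.
- **SAP, Adverse events:** use the protocol's relatedness classes, which are unrelated, drug, device and technical procedure.

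The cost is one definition in each document and one added class in the SAP. No new event data are needed: protocol 9.3 records date and time of onset from consent, and 6.4.2 already records events separately before anaesthesia and after the procedure. The one item to confirm is that induction time can be taken from the operating-room record, since the documents do not say that it is on the CRF.

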11 STUDY MONITORING - ACCESS TO SOURCE DATA

11.1 Definition & purpose

The Sponsor monitor or designee is responsible for establishing the schedule and procedures to be followed for monitoring this study. Monitoring will be made at regular intervals during the study. Prior to the beginning of this study, the Investigator will be informed as to the anticipated frequency of the monitoring visits. In addition, the Investigator will receive due notification prior to each monitoring visit during the course of the study.

The purpose of these visits is to verify:

1. The informed consent process is properly documented
2. The reporting of AEs and all other safety data
3. Adherence to the protocol
4. Maintenance of required regulatory documents
5. Study supply accountability
6. Completeness and accuracy of the CRF data and other data submitted

At each visit, the investigator will be expected to cooperate with the Sponsor's representative(s) for the review and verification of all CRFs, the drug supply and inventory records and any additional records that may have been previously arranged.

11.2 Source Data

The data corresponding to the VTP procedure will be recorded in a specific document provided by the Sponsor (VTP report form) and will be considered to be source data. The VTP report form collects all the technical information (power, energy, diffuser length, etc.).

If the study site uses electronic subject files then the participant' records will be printed, dated and signed by the Investigator. These records will be kept in the subject's study file and will be used for source data verification.

11.3 Pre-Study training

Pre-Study Visit

At the pre-study visit, the Sponsor or his designee will ensure that the investigator has the technical means and the staff to carry out the study with regard to availability, subject recruitment, facilities and environment.

Study initiation

The Sponsor or Sponsor's representative will provide training at study site on the study procedures and assessments prior to the start of the study; this training will occur as an individual site initiation visit.

Prior to the start of the study, the following information must be sent by the site to STEBA:

1. Protocol and financial agreement signed by all parties
2. Written approval from the IECs/IRBs
3. Curriculum vitae of the Investigator
4. Appropriate regulatory documentation.

11.4 Study Monitoring Visits

A study monitor will ensure the monitoring of the study at regular intervals.

At each monitoring visit, the CRFs will be 100% verified against the source documents to ensure adherence to the protocol and compliance of the site to the regulatory requirements. The monitor will also review the study medication records, regulatory documents and correspondence, perform study supply accountability and will periodically inspect the facilities to ensure that the sites study documentation, personnel and facilities remain adequate for the duration of the study. The monitor shall have access to the source documents and other information needed to ensure investigator compliance with the clinical investigation plan and applicable rules and regulations, and to assess the progress of the clinical investigation.

The monitor will address all the errors, omissions and issues with the Investigator and/or other appropriate study personnel, and will ensure that the appropriate corrective action is taken.

11.5 Study Termination Visit

At the end of the study, STEBA will be provided with:

1. Completed CRFs
2. Used and unused medications and remaining packaging. Unused bottles are to be kept refrigerated and protected from light until instruction from the Sponsor or the Sponsor's designee. They will be returned to the Sponsor unless written approval from the Sponsor authorizing the destruction.

12 QUALITY CONTROL AND QUALITY ASSURANCE

12.1 Good Clinical Practice

The study will be conducted in compliance with Good Clinical Practice as stated in the ICH Harmonised Tripartite Guidelines (CPMP/ICH/135/95), the declaration of Helsinki (see Appendix 1) all applicable state and local regulations.

12.2 Standard Operating Procedures

The study will be conducted according to pre-established written Standard Operating Procedures (SOP) of the Sponsor or its agents. The Quality Assurance personnel of the Sponsor or the Sponsor's designee may audit the clinical investigator's site at any time during the study. The investigator and his/her team must be available during such audits, allowing auditors to access to the technical site, study material, source data and subject's file. The subject's anonymity must be safeguarded and data checks during the audits must remain confidential.

12.3 Protocol Amendment Procedure

With the exception of emergency situations, no changes or deviations in the conduct of this protocol will be permitted without the documented approval of the Sponsor.

The IRB/IEC which granted the original approval for the study must be notified of all changes in the protocol and must provide documented approval of any change or deviation which may increase the risk to the subject and/or which may adversely affect the rights of the subject or validity of the investigation.

This stipulation does not apply to those changes made to reduce discomfort or potential risk to the subjects.

In the event of any emergency, the investigator will perform all medical procedures which he deems appropriate. However, all such procedures must be promptly reported to the Sponsor.

12.4 Anonymity of Subject Identification

Each subject selected in the study will be assigned a sequential 'selection number'. The subject selection number will consist of seven digits, which will reflect ISO code of the country, the centre number and the subject number in the centre. The first subject selected for screening in a country ISO code XXX in a centre 01 will be subject number XXX-01-01. Additional subjects will be assigned sequential numbers: XXX-01-02, XXX-01-03, etc. This subject number is captured in the CRFs.

This 'selection number' differs from the treatment number(s) that will be assigned and reported in the CRF on the day of the VTP procedure.

If a subject is not eligible to receive the treatment and is considered a screen failure, the subject selection number may not be reassigned.

12.5 Subject's Written Information and Participation Agreement

The risks and benefits of participating in the study will be explained to each potential subject prior to entering the study. The informed consent will be written in a language style readily understood by the subject. The informed consent must be approved by the IRB/IEC prior to the initiation of the study, the performance of any study procedure and the dispensing of any study medication. The Principal Investigator or his/her designee must obtain a signed Informed Consent Form for each subject. Receipt of the signed Informed Consent Form will be documented in the CRF and the original will be retained by the Investigator. A copy of the signed Informed Consent Form will be given to each subject. If the Informed Consent Form is amended during the course of the study, subjects will be asked to renew its consent to the updated consent form and given a signed copy.

12.6 Confidentiality of Trial Documents and Subject Records

The information in this protocol and any further documentation contains trade secrets and commercial information that are privileged or confidential and may not be disclosed unless such disclosure is required by law or regulations.

In any event, persons to whom the information is disclosed must be informed that the information is privileged or confidential and may not be further disclosed by them.

Subject's identity and personal data will be processed for this study and considered as strictly confidential. None of this personal information will be revealed in study documents assigned to third people or intended for publications. For legal requirements, any medical records needed for this study that identify the subject by name will be available to the employees and agents of the Health Authorities or any other governmental or regulatory authorities. This information will also be available to authorized study representatives from the Sponsor of this study.

13 ETHICS

The study will be conducted in accordance with the Declaration of Helsinki and its most recent amendments and in compliance with Good Clinical Practice (GCP). The informed consent document(s), any protocol amendments and any other appropriate study-related documents will be reviewed and approved by the required independent ethics committee(s) (IEC) and/or institutional review board (IRB) before implementation.

Informed consent will be obtained prior to the conduct of any study-related procedures.

